9.4 DATA SOURCES

MDV clinical database is health insurance claim database. As of end of February 2016, MDV has accumulated commercial claims database for both in and outpatients consisting of medical administrative claims records from more than 12.94 million patients from 230 large acute care DPC hospitals. Lab results are also available but number of hospitals providing with lab test results are limited.

Study period is from 14 Mar 2010 to 30 June 2016 in MDV database at the time of study protocol approval.

The MDV database is broadly representative of the Japanese population with similar distribution compared to the Japanese general population. There is research experience using the data, 19 publications, 5 conference presentations (as of Aug 2015).

9.5 STUDY SIZE

This study plans no formal hypothesis testing. The planned analyses are descriptive in nature and results of statistical tests are to be interpreted in an exploratory manner. For each treatment group, the available sample size is determined by feasibility assessments of the previous study 1160.279 according to the pre-specified time window and inclusion/exclusion criteria, and not by formal sample size justifications. Therefore, the purpose of the power assessments described in this section is to illustrate the precision of the effect estimates that can be achieved given the feasible sample size.

The expected sample size of dabigatran new starters meeting inclusion/exclusion criteria after matching has been estimated to be 4,427 from the previous study 1160.279. This expected sample size is considered to have sufficient precision, defined as having less than 10% chance of the upper bound of 95% confidence interval of hazard ratio (HR) exceeding 1.378, which was an FDA recommended non-inferiority margin for effectiveness at the planning stage of RE-LY study.

Hori et al reported that the incidence of stroke and systemic embolism in the Asian subgroup of RELY study was 3.06%/year (53 events/926 patient year).¹¹ In the feasibility study (CTMS 1160.279), the percentage of patients receiving high dose of dabigatran or 300 mg per day was 21% and the rest or 79% was receiving equal to or less than 220mg per day. According to the Asian subgroup reported by Hori, the observed hazard ratio of warfarin to dabigatran for the endpoint of stroke and systemic embolism was 0.45 and 0.81 for 300mg and 220mg daily dose group respectively. The combined assumed hazard ratio for MDV database will therefore be $\text{Exp}(\log(0.45) \times 0.21 + \log(0.81) \times 0.79)$ or 0.716.

Table 9 Sample size calculation

| follow-up(y) | N per group | Event Rate (/y) | NI Margin | Power (non-inferiority) |
|--------------|-------------|-----------------|-----------|---|
| 0.40487 | 4421 | 0.025 | 1.378 | 0.987 0.944 0.846 0.692 0.507 |
| 0.40487 | 4421 | 0.025 | 1.378 | |
| 0.40487 | 4421 | 0.025 | 1.378 | |
| 0.40487 | 4421 | 0.025 | 1.378 | |
| 0.40487 | 4421 | 0.025 | 1.378 | |
| 0.40487 | 4421 | 0.03 | 1.378 | 0.996 0.974 0.905 0.770 0.583 |
| 0.40487 | 4421 | 0.03 | 1.378 | |
| 0.40487 | 4421 | 0.03 | 1.378 | |
| 0.40487 | 4421 | 0.03 | 1.378 | |
| 0.40487 | 4421 | 0.03 | 1.378 | |
| 0.40487 | 4421 | 0.035 | 1.378 | 0.999 0.988 0.943 0.832 0.650 |
| 0.40487 | 4421 | 0.035 | 1.378 | |
| 0.40487 | 4421 | 0.035 | 1.378 | |
| 0.40487 | 4421 | 0.035 | 1.378 | |
| 0.40487 | 4421 | 0.035 | 1.378 | |

Assuming stroke/SE event rate of 0.03/PY and HR of 0.716, the probability of the upper bound of 95% CI exceeding 1.378 is considered to be less than 10%. Lower event rate or narrower margin will reduce power.

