9.7 DATA ANALYSIS

9.7.1 Main analysis

Propensity Score Matching

[figure not shown]
To reduce channelling bias, dabigatran and warfarin study groups will be established using PS matching method, on a 1:1 fixed ratio. The nearest neighbour method of propensity score matching within a caliper of 0.10 of the standard deviation of the estimated logit will be used to select the matched samples. All pre-defined variables has been evaluated in CTMS 1160.279 for inclusion into the model. Covariates with less than 10 patients present in the data was eliminated as well as CHADs which showed high co-linearity with CHADsVASC which was eliminated from the model. Otherwise, all pre-defined variables will be used. For further detail of the methodology of PS matching, please see the study protocol CTMS 1160.279.

For the primary outcome

Incidence rates of each treatment cohort (warfarin and dabigatran) will be provided, and all analysis will be conducted on the PS matched sample. The hazard ratio (HR) of stroke/systemic embolism for the dabigatran cohort as compared to the warfarin cohort and its 95% confidence interval (CI) will be estimated from the PS matched cohort using a Cox regression model with treatment group as the dependent variable. No additional covariates are considered in the Cox model as no residual imbalance was identified after PS matching (1160.276 study report, c15432368)." There will be no formal hypothesis testing. Kaplan Meier analysis with the number of patients at risk during the follow-up period after the index date and the number of events for ischemic stroke and major bleeding will be provided.

For the secondary outcome

Same analysis method will be utilized to calculate HR for the outcome of major bleeding.

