9.9 LIMITATIONS OF THE RESEARCH METHODS

- Unobservable factors or factors not captured in the database such as laboratory data not equally distributed in the treatment groups that may also influence the outcomes could lead to unobserved confounding.
- The anticipated sample size might be limited which might lead to imprecise results. Therefore the study can only be considered to be exploratory. Based on the expected small sample size there is also the risk of pure chance findings. No hypothesis testing is planned,
- All information of each patient is from consent giving DPC hospitals. If patients have visits to other non-DPC medical institutions, these data are not included in the MDV data.

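### Section 9.5 presents non-inferiority power under an assumed benefit as precision, and its below-10% figure comes out at about 11–12% at the planning hazard ratio

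*Combined protocol and SAP*

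**What the plan says.** Section 9.5 explains that the sample size comes from a feasibility study and that the power figures serve "to illustrate the precision of the effect estimates that can be achieved given the feasible sample size". It then judges the size adequate: "This expected sample size is considered to have sufficient precision, defined as having less than 10% chance of the upper bound of 95% confidence interval" for the HR lying too high, which it specifies as "exceeding 1.378, which was an FDA recommended non-inferiority margin for effectiveness at the planning stage of RE-LY study".

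The planning HR is a weighted combination of two dose-specific HRs and equals 0.716. Table 9 uses 4,421 patients per group, 0.40487 years of follow-up, a margin of 1.378 and event rates of 0.025, 0.03 and 0.035 per patient-year. Its last column is labelled as non-inferiority power. The sentence after the table concludes that, at 0.03 per patient-year and HR 0.716, the chance of the upper bound passing 1.378 is below 10%.

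Section 9.7.1 plans an HR for which "its 95% confidence interval (CI) will be estimated from the PS matched cohort using a Cox regression model", and adds: "There will be no formal hypothesis testing". Section 9.9 warns: "The anticipated sample size might be limited which might lead to imprecise results". The visible text gives no expected interval width.

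**The concern.** The precision of an HR estimate is the width of its confidence interval, which depends mainly on the number of events. The criterion in 9.5 depends as much on where the true HR is assumed to lie. If the assumed HR is far enough below 1.378, a wide interval still clears the margin. A high value therefore does not show that the HR will be estimated tightly.

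The below-10% conclusion is also stated for HR 0.716, while the nearest Table 9 entry above 0.90 at 0.03 per patient-year (0.905) appears to belong to a slightly lower HR.

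Section 9.5 is where a reader of the report or the planned manuscript would look to learn how much the HR estimate can bear. It currently offers a label and a probability that do not answer that question, and the probability is slightly too favourable.

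**Working it through.** **Inputs, all from 9.5 and Table 9.** N = 4,421 per group; follow-up 0.40487 years; margin 1.378; rate 0.03 per patient-year; planning HR 0.716, confirmed as exp(0.21 × ln 0.45 + 0.79 × ln 0.81) = 0.716. The allocation is 1:1 and the interval is two-sided 95% (9.7.1). No HR column is visible in the extracted Table 9, so the HRs below are inferred.

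**Step 1. Reproduce Table 9.** Patient-years per group: 4,421 × 0.40487 = 1,789.9. With the rate applied to warfarin and rate × HR to dabigatran:

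- expected events D = 1,789.9 × rate × (1 + HR)
- SE(log HR) = 2/√D
- P(upper bound < 1.378) = Φ( ln(1.378/HR)/SE − 1.96 )

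At 0.03 per patient-year:

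| HR (inferred) | D | Computed | Table 9 |
|---|---|---|---|
| 0.5 | 80.5 | 0.995 | 0.996 |
| 0.6 | 85.9 | 0.971 | 0.974 |
| 0.7 | 91.3 | 0.899 | 0.905 |
| 0.8 | 96.7 | 0.762 | 0.770 |
| 0.9 | 102.0 | 0.576 | 0.583 |

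All 15 entries, over the three rates, agree within 0.01. Table 9 is therefore non-inferiority power at one-sided 0.025, and 0.905 is the HR 0.70 entry.

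**Step 2. Does the probability track precision?** The 95% CI runs from HR/k to HR × k, with k = exp(1.96 × 2/√D).

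- HR 0.5: D = 80.5, k = 1.55, probability 0.996 in Table 9.
- HR 1: D = 1,789.9 × 0.03 × 2 = 107.4, k = 1.46, probability Φ(0.3206/0.1930 − 1.96) = 0.38.

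On the ratio scale the interval is wider at HR 0.5, yet the probability is far higher. Between these two cases it moves against precision.

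**Step 3. The stated conclusion at HR 0.716.** D = 1,789.9 × 0.03 × 1.716 = 92.1 (53.7 warfarin + 38.4 dabigatran). SE = 2/√92.1 = 0.208. ln(1.378/0.716) = 0.655.

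- P(upper bound < 1.378) = Φ(0.655/0.208 − 1.96) = 0.881, so the chance of passing 1.378 is 11.9%.
- Raising D by 2.1%, to match Table 9's own entries, gives 0.888, or 11.2%.
- Linear interpolation between the Table 9 entries for 0.7 and 0.8 gives 0.905 − 0.16 × (0.905 − 0.770) = 0.883, or 11.7%.
- A Poisson simulation gives 0.878, or 12.2%.

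**Step 4. Other readings of 0.03 per patient-year.**

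- Rate in both arms, or their average: D = 107.4, chance of passing 1.378 = 7.6%.
- Rate in the dabigatran arm: D = 53.7 × (1 + 1/0.716) = 128.7, chance = 4.0%.

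Neither reading reproduces Table 9 at round HRs. At HR 0.7 they give 0.939 and 0.972 against the printed 0.905.

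**Step 5. Other event rates, HR 0.716, rate applied to warfarin.** The chance is 18.2% at 0.025 and 7.6% at 0.035.

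**Step 6. Expected precision of the planned estimate.** k = exp(1.96 × 0.208) = 1.50, so the expected 95% CI at HR 0.716 is 0.476 to 1.077.

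**The case against.** The best defence is that 9.5 defines its criterion openly, and that the criterion is a genuine property of the interval that 9.7.1 will report. The 1.378 value can serve as a reference point for reading that interval, and its origin is stated. The size is admitted to be feasibility-based, the study is called exploratory, the text after Table 9 concedes that a lower event rate would reduce power, and 9.9 warns of imprecision. All of this stands, and it keeps the point modest.

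Two stronger readings are tempting. A reader might infer that the sizing is invalid because it belongs to a comparison the plan does not make. The documents do not support that: where the upper bound falls is a fair descriptive question about the planned interval.

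A reader might also compute the chance that the interval excludes 1 at HR 0.716, which is Φ(0.334/0.208 − 1.96) ≈ 36%, and set it against the claimed 90% as proof that the design fails. Those are different quantities, and no superiority test is planned. The 36% illustrates what about 92 events can show and is not a failed criterion. Nor does any passage say that an interval including 1 would be read as no difference.

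The absent HR column may be lost in text extraction and is not held against the plan.

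What the defence does not answer is that 9.5 promises precision without giving a width, and that its own below-10% figure does not follow from its own table's formula.

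**Conclusion.** The point holds in a limited form. Section 9.5 labels as precision a probability that is high because a benefit is assumed: 0.996 at HR 0.5 with a CI factor of 1.55, against about 0.38 at HR 1 with a factor of 1.46. The below-10% conclusion at HR 0.716 and 0.03 per patient-year is narrowly missed, at about 11–12%.

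This rests on the inferred HRs of 0.5 to 0.9 and on the rate applying to warfarin, the reading that reproduces all 15 entries. Below 10% would hold if 0.03 were the rate in both arms or their average (about 8%) or the dabigatran rate (about 4%), but neither fits the table. The 4,427 in the text of 9.5, used in place of 4,421, gives 11.8% and changes nothing.

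The documents do not support saying that the design fails a planned test or that its estimator is wrong. The defect is one overstated figure and a missing interval width.

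**What to change.** In 9.5, replace the sentence on sufficient precision and the below-10% conclusion after Table 9 with:

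- the expected precision of the planned estimate: about 92 events, and a 95% CI of about HR/1.5 to HR × 1.5, or 0.48 to 1.08 at HR 0.716;
- the probability that the upper bound passes 1.378, restated as about 11–12% at HR 0.716 and 0.03 per patient-year, and labelled as conditional on the assumed HR;
- the arm to which the event rate applies.

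Table 9 can stay under the same conditional label, with the HR shown for each row if the original does not already show it. The 36% chance of excluding 1 may be added as an illustration only, with a note that no superiority test is planned.

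The cost is a less favourable precision statement. No patients, data, design element or estimator changes.

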Several real world evidence studies have been published recently to compare effectiveness and safety of dabigatran, rivaroxaban and apixaban using claims database from the U.S., Danish and Taiwan national claims databases.²⁻⁵ In addition, several validation studies have been reported using DPC hospital claims database. Yamaguchi et al assessed the positive predictive value (PPV) of MDV claims defined event definitions for deep vein thrombosis, pulmonary embolism and bleeding events against clinical diagnosis of a panel of experts who examined claims codes and reached a consensus.⁶ Although sample of events were relatively small (50 for each event) PPV for thromboembolic events was 75% and bleeding events was 73.3%. Yamana et al evaluated the DPC data identified Charlson co-morbid conditions from 4 mid-size acute care hospitals against chart review diagnosis for the validity of claims defined diagnosis.⁷ Specificity was found to be over 96%, although sensitivity was below 50%. PPV for cerebrovascular disease diagnosis was reported to be 86.4% with negative predictive value of 93.5%. Koretsune et al conducted a validation study on MDV database to calculate the PPV for stroke, systemic embolism (SE) and intracranial hemorrhage (ICH) utilizing methodology similar to that reported by Yamaguchi et al, and found the PPV of stroke, SE events (SEE) and ICH to be 74%, 26.7% and 85.0%.⁸ Second evaluation of SEE after changing claims definition increased the PPV to 86.7%.

There has been no comparative effectiveness or safety analysis of dabigatran vs. warfarin has been published using large scale Japanese claims database thus far.

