9.3.2 Outcomes

9.3.2.1 Primary Outcome

- Outcome name: stroke and systemic embolism
- Time frame: drug exposure period
- Safety issue. N/A
- Definition: definition of stroke and systemic embolism provided in Koretsune et al will be used for this study⁸ as following.
 - ✓ Stroke: all three following conditions must be met:
 - [1] Imaging (magnetic resonance imaging (MRI) or computed tomography (CT)) is performed after a diagnosis code of atrial fibrillation.
 - [2] Diagnosis of stroke defined as I60-I64 occurs in the same month as the imaging
 - [3] Either of the following condition is met:
 - A) Rehabilitation for cerebrovascular disease within 30 days from the date of imaging
 - B) Death within 30 days from the date of imaging
 - ✓ Systemic embolism events:
 1. Retinal vascular occlusions: three following conditions must be met:
 - [1] Ophthalmic examination is performed after the date of definitive diagnosis of atrial fibrillation or cardioembolic stroke (including the day of the diagnosis).
The second or later ophthalmic examination during the same hospitalization is excluded.
 - [2] Diagnosis of retinal vascular occlusion in the month of the date of ophthalmic examination.
 - [3] The following A) and B) are satisfied:
 - A) Prescription of anticoagulant/antiplatelet agents on the day of ophthalmic examination or the next day
 - B) Non-prescription of anticoagulant/antiplatelet agents within 30 days from the date of ophthalmic examination.
 2. Other than retinal vascular occlusions: four following conditions must be met:
 - [1] Imaging: MRI, CT, roentgenography (using a contrast medium) or vascular echo is performed after the date of definitive diagnosis of atrial fibrillation or cardioembolic stroke (including the day of the diagnosis).
 - [2] Systemic embolism (including the name of injury/disease at the time of admission) is diagnosed and recorded as the name of the disease during hospitalization in the month of the date of imaging.
 - [3] The date of imaging or the next day: Treatment
Either of the following conditions is satisfied:
 - A) Treatment with heparin at >5,000 units or thrombectomy on the day of imaging or the next day
 - B) Death within 30 days from the date of imaging

✓ [4] Fees for emergency medicine administration or specific intensive care management on the day of imaging are calculated.

Intracranial bleeding: all four following conditions must be met:

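### The precision claim and the primary HR treat every claims-defined stroke/SE event as true, although the plan cites a stroke PPV of 74%. The effect of false events on the HR and on the 1.378 benchmark should be quantified as a range.

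*Combined protocol and SAP*

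**What the plan says.** - **Outcome.** Section 9.3.2.1 takes its stroke and SE algorithms from a validation study in the same MDV database ("Definition: definition of stroke and systemic embolism provided in" that study).
- **Validity.** Section 7 says of that study that it "found the PPV of stroke, SE events (SEE) and ICH to be 74%, 26.7% and 85.0" per cent. For SE it adds: "Second evaluation of SEE after changing claims definition increased the PPV to 86.7" per cent. It gives no PPV for the stroke/SE composite and none by treatment arm.
- **Precision.** Section 9.5 calls the sample size "considered to have sufficient precision, defined as having less than 10% chance of the upper bound" of the 95% CI "exceeding 1.378, which was an FDA recommended non-inferiority margin for effectiveness at the planning stage of RE-LY study". Its closing sentence says that, at 0.03/PY and HR 0.716, the chance of "the upper bound of 95% CI exceeding 1.378 is considered to be less than 10" per cent. Both the rate and the HR are based on a RE-LY subgroup. There is no allowance for false events.
- **Analysis.** The visible section 9.7.1 plans a Cox model with treatment group only, on the claims-defined outcome.
- **Limitations.** Sections 9.9 and 9.12 deal with unobserved confounding, and 9.9 also with sample size and with care outside the participating hospitals. Neither mentions misclassified outcomes.

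**The concern.** A stroke PPV of 74% means that about one counted stroke in four is not a stroke. If those false events are unrelated to the drug, they add a similar background rate to both matched arms and move the HR towards 1. The plan reports the size of this measurement error and then does not use it, either in the precision statement or in the analysis.

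The stake is interpretation. The sponsor ties sufficient precision to 1.378 and plans a publication (section 12), so readers will compare the reported upper bound with 1.378. That comparison is for claims-defined events. Whether it carries over to true strokes depends on how the false events are spread between the arms, and the plan is silent on this.

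**Working it through.** **Inputs.** From Table 9: 4421 per group, 0.40487 years of follow-up, margin 1.378. From the text of 9.5: rate 0.03/PY, HR 0.716. From section 7: PPV 74% (stroke) and 86.7% (SE, revised definition). Person-years per arm = 4421 × 0.40487 = 1789.9. Events in the warfarin arm at 0.03/PY = 53.7.

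**Step 1: the plan's own figure.** With E = 53.7 × (1 + HR), power = Φ(ln(1.378/HR) × √E/2 − 1.96). The HR column of Table 9 is not readable in the text available. An inferred grid of 0.5, 0.6, 0.7, 0.8, 0.9 gives 0.995, 0.971, 0.899, 0.762, 0.576 at 0.03/PY, against the printed 0.996, 0.974, 0.905, 0.770, 0.583. All 15 cells agree within 0.9 percentage points.

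At HR 0.716: E = 92.1, ln(1.378/0.716) = 0.655, power = 0.881. The chance of exceeding 1.378 is therefore 11.9%. With a Wald standard error, √(1/53.7 + 1/38.4), it is 12.7%. If 0.03 is instead read as the overall rate, it is 7.6%, but that reading fits Table 9 less well.

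**Step 2: effect of false events on the HR.** With equal sensitivity, HR_true = HR_obs × PPV_dabigatran / PPV_warfarin. The PPV level alone fixes nothing; the ratio between the arms matters.

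- *Equal PPV in both arms:* ratio 1, no bias, and 1.378 stays 1.378.
- *Equal absolute false-event rate:* HR_obs = PPV × HR_true + (1 − PPV), with PPV that of the warfarin arm.
  - True 0.716 at PPV 74%: 0.74 × 0.716 + 0.26 = 0.790.
  - Observed 1.378 at PPV 74%: (1.378 − 0.26)/0.74 = 1.511.
  - Observed 1.378 at PPV 86.7%: (1.378 − 0.133)/0.867 = 1.436.
  - If 74% is pooled over both arms, the false rate relative to the observed warfarin rate is 0.26 × 2.378/2 = 0.309, and HR_true = (1.378 − 0.309)/(1 − 0.309) = 1.547.
- *Differential PPV (illustration, setting 74% against 86.7%):* 1.378 × 0.867/0.74 = 1.61 if warfarin has the lower PPV, and 1.378 × 0.74/0.867 = 1.18 if dabigatran has.

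**Step 3: chance that the raw upper bound exceeds 1.378 at a true HR of 0.716.** Each cell gives the step 1 formula, then the Wald version.

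| Scenario | Formula of step 1 | Wald |
|---|---|---|
| No misclassification | 11.9% | 12.7% |
| Dilution, PPV 74%, 0.03/PY is the observed warfarin rate (E = 96.1) | 22.1% | 22.7% |
| Dilution, PPV 74%, 0.03/PY is the true rate with false events added (rate 0.03/0.74, E = 129.9) | 11.3% | 11.7% |
| Equal PPV 74%, 0.03/PY true, false events added (E = 124.5) | 4.5% | 5.0% |

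**Step 4: when dilution is anti-conservative.** At a true HR of 1.378 the raw upper bound falls below 1.378 in 2.5% of studies if there is no misclassification. With dilution at PPV 74% the observed HR is 0.74 × 1.378 + 0.26 = 1.280. The chance becomes 6.0% (E = 122.4) or 6.9% (E = 165.4) under the two readings of the rate. At a true HR of 0.716 dilution moves the estimate up, towards the benchmark.

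**The case against.** **PPV does not fix the direction of bias.** This stands. A reader might infer from a PPV of 74% that the HR is pulled towards 1 and that 1.378 really means 1.51. The documents do not support that as a fact. It needs equal absolute false-event rates, equal sensitivity, and 74% as the warfarin-arm PPV, and none of these is stated. Equal false-event rates are a reasonable scenario in matched arms: the stroke rule has no washout for earlier stroke, and stroke/TIA history is in the propensity score. It remains an assumption.

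**Dilution does not make 1.378 easier to meet under the plan's own HR.** This also stands. A reader might infer that it always does, but step 4 shows that this holds only for a true HR above 1.

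**The gap from the stated 10% is not all misclassification.** Correct: the baseline is already about 12-13% when 0.03 is the warfarin rate. A reader might also compute the chance of failing to exclude a *true* HR of 1.378 (observed limit below 1.280), about 34-35% or 21-22%, and set it against the stated 10%. Section 9.5 makes no claim about that quantity, so the comparison is not like for like.

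**The bleeding figure does not carry over.** Section 7 says that "PPV for thromboembolic events was 75% and bleeding events was 73.3" per cent, but this comes from another validation study with about 50 sampled events of each type. Section 9.3.2.2 sets its own major-bleeding definition and does not adopt that study's.

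**The study is exploratory, and part of the plan is hidden.** There is no formal test, so no decision rule fails. The contents list shows a redacted entry directly after 9.7.1, so the lack of a bias analysis can be stated only for the visible text. Neither point explains why 9.9 and 9.12 omit outcome misclassification.

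**Conclusion.** The concern holds as a gap in interpretation. The plan adopts algorithms with a cited stroke PPV of 74%, judges precision as if all events were true, and leaves outcome misclassification out of its visible limitations.

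The size depends on assumptions. With equal false-event rates and equal sensitivity, an observed 1.378 corresponds to a true HR of about 1.44 to 1.55 (1.51 at a warfarin-arm PPV of 74%), and a true 0.716 appears as about 0.79. With equal PPV and sensitivity there is no bias. Differential error could go either way. The 74% is for stroke alone, and using 86.7% as the upper end assumes that the SE algorithm written out in 9.3.2.1 is the revised one.

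At the planned HR the raw upper bound exceeds 1.378 with a chance of about 12% to 23% under dilution, compared with about 12-13% without it and the stated figure below 10%. The wide range comes mainly from whether 0.03/PY means true or claims-counted events, which section 9.5 does not say.

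**What to change.** - **9.7.1:** unless the redacted section already has one, add a quantitative bias analysis for stroke/SE as a sensitivity analysis beside the raw HR. Cover a PPV range, for example 74% to 87%, under three scenarios: equal false-event rates, equal PPV, and differential PPV in both directions. Do not report a single corrected HR from the equal-false-rate formula. That formula always moves the estimate away from 1 (an observed 0.79 becomes 0.716), and it rests on unverified assumptions.
- **9.5:** say whether 0.03/PY is a true or a claims-counted rate and whether it is the warfarin or the overall rate. Restate the chance of exceeding 1.378 accordingly, and say that 1.378 is applied to the HR for claims-defined events.
- **9.9:** add outcome misclassification, with the PPVs already cited in section 7.
- **Major bleeding:** label any scenario that uses 73.3% as illustrative only.

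The cost is a few lines of text and one small analysis on existing data. The downside for the sponsor is a less favourable stated precision and a wider range around the primary result.
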